3) Study period II Treatment (Day 0 to 84): Visits 2 through 9. This is the 12-week period of double-blind placebo-controlled acute treatment. At day 0, EKG for safety monitoring will be conducted. The baseline mRNA sample will be collected. All subjects who continue to meet eligibility criteria will be randomized to one of two groups: Vortioxetine or placebo. Randomization will be performed at a 1:1 ratio into two treatment groups, and both vortioxetine and placebo will be distributed to the patient in blister packs. If a participant is taking 10mg of vortioxetine they will be provided with 2 blister packs at each visit. If a participant is taking 20mg, they will be provided with 4 blister packs. Surrogate marker testing for psychophysiology, mRNA, and neuropsychological testing will be repeated at the completion of the double-blind treatment. Due to the amount of study procedures for certain study visits, we will allow study visits to be done over two days.

4) Follow-Up (Day 84 to 98): Visit 10. Patients will return to the clinic two weeks after the last dose of study medication for assessment of psychiatric status, suicidality, follow-up of any abnormal laboratory or EKG results, and to assist with transition of psychiatric care, if indicated.

See the **Schedule of Events** chart at the end of this section for details of the procedures performed during each visit.

B. Justification of Sample Size

Power Analysis:

Samples of n=60 (2 groups) are associated with reduced but adequate power. Between group differences in change scores of $d=.70$ are detectable with .80 power at $p<.05$. Correlations of

.33 between two variables are detectable with power=.80 in the full sample of 60. Within treatment conditions (n=30) correlations of $r=.50$ are detectable with the same level of power.

C. Informed Consent, Regulatory and Ethical Considerations

The study will be conducted in accordance with Good Clinical Practices (GCP), 21CFR Parts 50 and 56 and all applicable regulatory requirements. Approval for conduct of the study will be obtained from the institutional review boards at both sites.

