Study Period II is the 12-week double-blind treatment period. On the day of randomization, an EKG and laboratory tests (blood samples for CPK and a urine sample for pregnancy testing) will be collected.

Patients will be assessed in-person weekly or every other week from Visit 2 through Visit 9, using self-report and clinician-administered measures to gauge changes in symptomatology (see Schedule of Events chart below). In order to maximize patient retention and account for unpredictable schedules, the treatment window will consist of the target visit date plus/minus 2 days for Visit 2 through Visit 4 and plus/minus 3 days for Visit 5 through Visit 10. Patients will be randomized at a ratio of 1:1 to receive either Vortioxetine at a starting dose of 10 mg /day or placebo. Concurrent treatment with other psychotropic medication will NOT be permitted during the study with the exceptions of the hypnotics zolpidem, eszopiclone, zaleplon, and diphenhydramine. Patients taking diphenhydramine will be instructed not to take any doses of this medication for three days prior to the visits that involve Neuropsychological testing or the Startle Task. These hypnotics will be allowed up to 3 doses per week during the trial. The CBC, blood chemistries, serum pregnancy, thyroid function measures and urinalysis will also be repeated at week 12. At the end of this study period, the neurophysiology, neuropsychological, and mRNA measures will be repeated. Patients will be outpatients for the duration of the study. Due to the amount of study procedures for certain study visits, we will allow study visits to be done over two days.

Dosing of Study Medication: All patients will be started on 10 mg vortioxetine/day (or placebo equivalent) dosed in the morning with food. Patients experiencing sedation from the medication may be switched to evening dosing at the discretion of the study psychiatrist. If by Week 4 the patient has demonstrated inadequate benefit from the medication, the dose will be increased to 20 mg/day. Patients unable to tolerate the 20 mg/d dose may be reduced to 10 mg/day between weeks 4 and 8. Patients unable to tolerate 10 mg will be discontinued from the trial. The dose of study medication should remain stable for weeks 8-12.

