Suicidal ideation is assessed at each study visit with the Columbia Suicide Severity Rating Scale (CSSRS), an instrument endorsed by the FDA for clinical trials. This brief instrument systematically tracks suicidal ideation and behavior (e.g., suicide attempts, wish to die, thoughts of suicide, and plan and intent), and classifies events according to the following categories: **Suicidal events** – *completed suicide, suicide attempt, preparatory acts toward imminent suicidal behavior and suicidal ideation.* **Non-suicidal events** – *self-injurious behavior, no suicidal intent and other, no deliberate self-harm.* **Indeterminate or potentially suicidal events** – *self-injurious behavior, suicidal intent unknown.* Subjects who are considered by the study psychiatrist to be at high risk for suicide are discontinued from the study and referred for hospitalization and further treatment as clinically indicated.

Poor Adherence: Every effort will be made to encourage subject compliance with the dosage regimen as per the protocol. A record of the supplies dispensed, taken and returned will be recorded at each visit. Compliance will be monitored by pill counts. Subjects who miss three or more consecutive days of Vortioxetine during the study are considered non-compliant and will be counseled about need for adherence. Patients found to miss three consecutive doses of study medication twice will be withdrawn from the study. Non-adherent patients are classified as dropouts in the analysis.

Drop-outs: Drop-outs will be defined as randomized subjects lost to follow-up who do not complete the 12-week double-blind treatment period. Randomized subjects who drop out prior to completing one post-randomization efficacy assessment will not be included in the primary efficacy analysis.

SCHEDULE OF EVENTS											
Visit Number	S1	V1	V2	V3	V4	V5	V6	V7	V8	V9	V10
Week (± 2 days for V2-V4, ± 3 days for V5-10)		-1	0	1	2	4	6	8	10	12	14
Day		-7	0	7	14	28	42	56	70	84	98
Informed consent	X										
Demographics/Hollingshead	X										
Vital signs	X	X	X	X	X	X	X	X	X	X	X
Weight	X		X			X		X		X	X
Psych/Medical eval. by MD	X									X	
Physical examination	X									X	
12-lead EKG	X		X							X	
MINI modules A, C-P	X										
Dispense Study Drug & Diary			X	X	X	X	X	X	X		
Laboratory Tests											
CBC	X									X	
Blood Chemistry	X									X	
Liver Function Tests	X									X	
GGT	X										
Urinalysis	X									X	
Urine drug screen	X										
Serum Pregnancy	X									X	

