Urine Pregnancy			X								
CPK			X							X	
TSH, Free T4	X									X	
Hepatitis B and C	X										
Pharmacokinetics						X		X		X	
Psychiatric Measures											
CAPS and CGI	X		X		X	X		X		X	
MADRS			X		X	X		X		X	
CSSRS	X		X	X	X	X	X	X	X	X	X
E-TRIP	X										
PCL-5/QIDS-SR			X		X	X		X		X	
CTQ & PDS Screen	X										
PSQI			X			X		X		X	
SDS	X		X				X			X	
Life Experiences Survey			X							X	
Safety Measures											
PRISE/Con meds			X	X	X	X	X	X	X	X	X
FIBSER				X	X	X	X	X	X	X	
Exploratory Aim Testing											
Startle Paradigm		X								X	
Genotype/Methylation			X							X	
Neuropsychological Testing: BACS + UPSAB		X								X	
mRNA			X							X	

Abbreviations: CAPS = Clinician-Administered PTSD scale; CBC = Complete blood count; CGI I/S = Clinical Global Impression Scale (improvement and severity); CSSRS = Columbia Suicide Severity Rating Scale; CTQ = Childhood Trauma Questionnaire; EKG = Electrocardiogram; ETRIP = The Emory Treatment Resistant Interview for PTSD; FIBSER = Frequency, Intensity and Burden of Side Effects Rating; GGT = Gamma glutamyl transpeptidase; Hollingshead= Hollingshead 4 Factors of Social Status Scale; MADRS= Montgomery Asberg Depression Rating Scale; PCL-5 =The Posttraumatic Stress Disorder Checklist for DSM-5; PRISE = Patient Rated Inventory of Side Effects; PSQI = Pittsburgh Sleep Quality Index; PDS = Post-traumatic stress Diagnostic Scale; PSSR = PTSD Symptom Scale Self Report; QIDS-SR = Quick Inventory of Depressive Symptoms; SDS = Sheehan Disability Scale; T4 = Thyroxine; TSH = Thyroid stimulating hormone;

Notes: Patients who terminate early will complete the Visit 9 safety and efficacy procedures.

I. Efficacy and Safety Tests and Procedures

1. Measures and Questionnaires

See **Appendix B** for a brief description of the rating scales.

2. Blood and Urine Tests for Safety

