1. DNA

We will draw DNA on all consenting subjects to evaluate whether carriers of identified risk alleles are associated with response or non-response to voritoxetine.

2. mRNA

We will draw 12 mls of blood at baseline and at week 12 to evaluate the expression of HPA-related mRNA expression.

3. Neurophysiology: Startle Testing

3a. Conditioning sessions. The following methods will allow us to assess fear acquisition, and conditional discrimination (learned safety), as well as the subjects' awareness of reinforcement contingencies in the experiment. The aversive stimulus (US) in these studies will be a 250 ms airblast with an intensity of 80 p.s.i. directed to the larynx as described in similar human fear conditioning studies (Grillon & Davis, 1997; Jovanovic et al. 2005). A compressed air tank connected to polyethylene tubing and controlled by a solenoid switch will emit the airblasts. The conditioned stimuli (CS's) used in the AX+/BX- session (A, B, C and X) will be different colored shapes; in the fear acquisition and extinction sessions the CS's will be neutral pictures. The CS's will be presented on a computer monitor. The pictures and colored shapes will be counterbalanced across subjects. The stimuli will be presented using SuperLab 3.0 for Windows (Cedrus, Inc.) and synchronized with the psychophysiological data acquisition using a DIO card (Measurements Computing, Inc). The psychophysiological data will be collected with Biopac MP150 (Biopac Systems, Inc.). Skin conductance will be acquired concurrently with acoustic startle.

3b. Acoustic startle. The acoustic startle response (eyeblink component) will be measured via electromyography (EMG) of the right *orbicularis oculi* muscle. Two 5 mm Ag/AgCl pre-gelled disposable electrodes will be positioned approximately 1 cm under the pupil and 1 cm below the lateral canthus. All resistances will be less than 6 kilo-ohms. EMG activity is acquired at a sampling rate of 1kHz, amplified and digitized. The startle probe (noise burst) will be a 108-dB [A] SPL, 40-ms burst of broadband noise with a near instantaneous rise time.

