Multiple outcome measures: To address the possible increase in Type I errors due to multiple outcome variables, we have a priori selected a single outcome measure (CAPS total) which will maintain the significance level (α) 0.05 for the primary analysis. For secondary outcome measures, we will adjust p-values by controlling for the false discovery rate (Benjamini & Hochberg, 1995) and report both unadjusted and adjusted p-values.

Random effects: Given that the majority of outcomes are behavioral in nature, we expect that there will be significant individual level variance that will need to be incorporated into the model. Thus our overall analysis approach will be to use linear 2-level mixed models or generalized linear mixed models, as appropriate, to analyze the repeated measures data with at least a random intercept to incorporate individual level variation. We will also incorporate a random slope if necessary however, it is not always necessary in our experience, particularly with scales with a limited range such as MADRS.

VIII. HUMAN SUBJECTS

Updated January 22, 2019

A. Subject Recruitment

Men and women between the ages of 18-65 with a primary diagnosis of PTSD using the DSM-V criteria will be eligible for the study. A total of 60 subjects will be randomized (30 to Vortioxetine and 30 to placebo). These subjects will be enrolled at 2 sites, Emory University School of Medicine and Miami Miller School of Medicine. Subjects will enter this study having been recruited through referrals from outpatient clinics, or referrals from other community clinics and community clinicians (psychiatrists, psychologists, and social workers) in the greater Atlanta and Miami regions. In addition, we will advertise locally in newspapers and radio and will post recruitment messages on internet sites.

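### The within-arm power figure in V.B (r=.50 at .80 power) uses all 30 randomised per arm, with no attrition allowance, although correlations of pre-to-post exploratory change need a Visit 9 test that is scheduled only at completion

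*Combined protocol and SAP*

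**What the plan says.** The Power Analysis in V.B rests on 60 patients in two groups. For associations inside an arm it says: "Within treatment conditions (n=30) correlations of $r=.50$ are detectable with the same level of power". VIII.A (Subject Recruitment) shows where the 30 comes from: "A total of 60 subjects will be randomized (30 to Vortioxetine and 30 to placebo". V.B has no dropout term.

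Other sections provide for patients leaving:

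- V.F (dosing): "Patients unable to tolerate 10 mg will be discontinued from the trial".
- V.H (Poor Adherence): "Patients found to miss three consecutive doses of study medication twice will be withdrawn from the study". V.H also ends participation for dangerous worsening, mania or psychosis, and certain serious adverse events.
- V.K (Pregnancy): a participant who becomes pregnant is withdrawn.
- VII.B (Missing data): the analysis is planned for randomised subjects who do not complete treatment.

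Startle, BACS/UPSA-B and mRNA sit in a separate exploratory block of the Schedule of Events. Each is measured twice, once at Visit 1 or 2 and once at Visit 9. V.A and V.F place the repeat at the end of double-blind treatment. For early leavers the schedule's notes say: "Patients who terminate early will complete the Visit 9 safety and efficacy procedures". V.K.1 lists what is done at discontinuation: efficacy evaluations, physical examination, EKG, vital signs, weight, laboratory measurements and adverse experiences. Neither text names startle or neuropsychological testing.

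The hypothesis under Exploratory Aim 2 (II) is that significant changes in cognition, functional capacity and quality of life will correlate across domains.

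**The concern.** A correlation between two changes can use only patients who have both the pre-treatment and the post-treatment value of each measure. The exploratory tests have no intermediate visit, so a patient who leaves without the Visit 9 test supplies no observed change. V.B nevertheless quotes sensitivity as if all 30 randomised patients in each arm supplied a pair.

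The r=.50 line is the only sensitivity that V.B states for within-arm associations. If the paired sample is clearly smaller than 30, a reader who takes the line at face value will think a null within-arm result more informative than it is.

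**Working it through.** **Inputs.** r=.50, n=30 and power .80 come from V.B; 30 randomised per arm from VIII.A. Alpha is .05. V.B does not give sidedness, so two-sided is assumed. The documents give no dropout rate, so losses of 10%, 20% and 30% are assumptions: 30 × .90 = 27, 30 × .80 = 24, 30 × .70 = 21 per arm.

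**Formulas (Fisher z).** Power = Φ(atanh(r)·√(n−3) − 1.960), with atanh(.50) = .5493. Required n = ((1.960 + .842)/atanh(r))² + 3. Detectable r at .80 power = tanh((1.960 + .842)/√(n−3)). Power was also computed from the exact bivariate-normal distribution of the correlation coefficient.

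**Step 1: reproduce the plan's figure.** At n=30: .5493 × √27 = 2.854; 2.854 − 1.960 = .894; Φ(.894) = .814. The exact value is .828. Required n is (2.802/.5493)² + 3 = 29.01. The stated figure is therefore correct at n=30. A one-sided test would give .887 at n=30 and need only 24, but the two-sided calculation is the one that matches the stated .80.

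**Step 2: repeat at smaller n.**

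| Pairs per arm | Loss | Power for r=.50, Fisher z | Power, exact | Detectable r at .80 power |
|---|---|---|---|---|
| 30 | 0 | .814 | .828 | .492 |
| 29 | 1 patient | .800 | .814 | .500 |
| 28 | 2 patients | .784 | .799 | .508 |
| 27 | 10% | .768 | .784 | .517 |
| 24 | 20% | .711 | .730 | .545 |
| 21 | 30% | .645 | .666 | .579 |

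For example, at n=24: .5493 × √21 = 2.517; 2.517 − 1.960 = .557; Φ(.557) = .711.

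**Step 3: slack.** By Fisher z, .80 is kept (to rounding) with one patient lost per arm; by the exact method, with two. Against .80 the shortfall is about 2 to 3 points at 10% loss, 7 to 9 at 20% and 13 to 16 at 30%.

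**Step 4: the pooled line, kept separate.** At the full n=60 the detectable r is tanh(2.802/√57) = .355, not the .33 that V.B states. That gap exists before any loss. With 10%, 20% and 30% loss (n = 54, 48, 42) the detectable r is .373, .395 and .421. Only the movement from .355 to these values is due to attrition.

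**The case against.** The strongest reply is that nothing in V.B is miscalculated on this line and that the plan names no smaller sample. VII.B includes every randomised participant who has baseline measures, through mixed models, and allows imputation of missing predictors. That is a fair limit. A reader might infer that the plan is certain to analyse a particular smaller number. The documents do not support this, because they give no dropout rate and withdrawal rules show only that loss is possible. However, VII.B does not restore the n of 30 either. The imputation is for predictors, and a patient with only a baseline exploratory value adds no observed change to a correlation of changes.

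A reader might also infer that early leavers are barred from the exploratory tests. No text says so. The reading rests on two lists that do not name them and on two statements that tie the repeat to the end of treatment. V.K.1 also mentions laboratory measurements without defining them.

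Third, V.B does not say which correlations the r=.50 line serves, and the Aim 2 hypothesis does not say its correlations are within arm. Several planned associations start from baseline markers: startle signatures, risk alleles, and pre-treatment expression and methylation (V.J). For a correlation of such a marker with CAPS change, an early leaver who attends a final visit still contributes. Genotype is collected under its own limit ("We will draw DNA on all consenting subjects"), but it needs no post-treatment test and its hypotheses compare groups, so it is not part of this point.

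Finally, the aims are labelled exploratory, and at 10% loss the figures barely move. Both observations stand and bear on severity.

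**Conclusion.** The point holds in a limited form. The r=.50 figure is correct for 30 pairs per arm, but 30 is the number randomised, V.B allows for no attrition, and the margin is one or two patients per arm. Within-arm correlations of pre-to-post change in cognition or functional capacity will have fewer than 30 pairs once patients leave without the Visit 9 test. The same applies to startle or mRNA change if it is correlated within arm.

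The size depends on an assumed loss. Power for r=.50 is about .77-.78 at 10%, .71-.73 at 20% and .64-.67 at 30%, and detectable r rises from about .49 at n=30 to about .52, .545 and .58. These values assume a two-sided .05 test, bivariate normality and no post-treatment exploratory test for early leavers.

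The documents do not support reading this as an arithmetic error in the r=.50 line, or as a defect in every within-arm association. The severity is minor: it concerns a stated sensitivity for exploratory aims.

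**What to change.** In V.B, state the assumed proportion of patients who will have both the pre- and post-treatment exploratory test, and give the detectable within-arm r at that number. Possible text: Assuming 20% of randomised patients have no Visit 9 exploratory test, about 24 per arm will provide a change score; a within-arm correlation of about r=.55 is then detectable with .80 power (two-sided .05). Put the 10% row (27 per arm, r about .52) and the 30% row (21 per arm, r about .58) beside it. Say that the line applies to correlations needing a Visit 9 exploratory measure, and not to baseline-marker or genotype associations with CAPS change.

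If the pooled line is restated too, first correct its full-sample value to .355 at n=60, then show .37, .395 and .42 at n = 54, 48 and 42, so that the two issues stay distinct.

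The cost is a rewording of V.B. It needs no extra patients, visits or procedures, and enrolment stays at 60. The downside is a slightly less favourable stated figure.

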(1) Screening Phase and (if necessary) Medication-Washout: Informed consent will be signed at the initiation of the screening phase. As part of the informed consent process, participants will be asked whether they are willing to have their research assessments videotaped, and to indicate their authorization for Audio/Video/Photography Recording on the

consent form. Patients refusing to consent to videorecording will still be permitted to participate in the study. Recordings of study visits will be used by the study team for interrater reliability training and assessment. Screening for psychiatric and medical eligibility will involve vital signs, weight, blood tests, pregnancy test, drug screen, psychiatric interviews, medical and psychiatric history, physical exam and electrocardiogram (EKG). We will also draw the genotype sample at this visit for consenting subjects.

If a patient is already taking medication for PTSD and has achieved therapeutic response, s/he will not be tapered off the effective medication(s) to participate in this study, and will not be eligible for the study. Patients who are taking a psychotropic medication that has proven ineffective for their PTSD symptoms will be tapered off the medication prior to randomization. Whenever possible, decisions to taper a patient's medication for the purpose of study participation will be made in conjunction with the patients' prescribing physician. Patients will be tapered off ineffective psychotropic medications over 7-21 days, though patients on fluoxetine or protriptyline will be required to be off those medications for 5 weeks prior to baseline. Risks associated with medication tapering will be discussed with the patient. This washout process will be conducted and monitored by the study physician.

(2) Study Period I – Pretreatment Testing (Days –7 to –1): Visit 1. During this study period, subjects will undergo surrogate marker testing (psychophysiology, and neuropsychological testing). These visits will be conducted over a 7-day period prior to the day of randomization, following the successful completion of all the screening procedures in Phase 1 above. We anticipate that these procedures can be completed in 1 study visit; however, we will be flexible to allow additional visits if required due to subject fatigue or time constraints.

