Medication compliance will be monitored by pill counts conducted at every visit during study period II. The patient will also maintain a medication diary to mark the date and time they took their medication. Women of child bearing potential will also use the diary to indicate the start date of their menstrual cycles, as this information will inform analysis of the startle testing data.

G. Follow-up

After participants completing the 12 week randomized treatment phase, they will return to the clinic 14 days later (Visit 10) for a follow-up evaluation. All subjects who complete the trial or discontinue the study because of lack of response or side effects will receive assistance in transitioning to another care provider as clinically appropriate at the research site (if they choose to do so), or will be referred back to their referring physician. Patients with clinically significant abnormal laboratory tests at Visit 9 will have those tests repeated at the follow-up visit.

H. Early Termination from Protocol

Medical or Administrative Reasons: Subjects will be terminated early if any of the following occur: (1) Intolerance to study drug in the dose range required by the study; (2) worsening of PTSD or depressive symptoms such that the subject's safety is endangered (e.g. suicidality); (3) If patient becomes manic or psychotic; (4) a serious adverse event (SAE) that is either: i) considered by the investigator to be possibly, probably, or definitely related to the study medication, or ii) places the subject at increased risk of harm if s/he were to continue in the study.

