Appendix B. Description of Scales

Brief Assessment of Cognition in Schizophrenia (BACS)

The Brief Assessment of Cognition in Schizophrenia (BACS) is a clinician-rated instrument that measures cognitive function. The domains of cognitive function that are assessed by the BACS include verbal memory, working memory, motor speed, attention, executive functions and verbal fluency. It is designed to require about 30 min of testing time. BACS A will be performed at V1 and Version B will be performed at V9.

UCSD Performance-Based Skills Assessment- Brief Version (UPSA-B)

The UCSD Performance-Based Skills Assessment (UPSA-Brief) is a role-play test designed to evaluate a person's functional capacity in two selected areas of basic living skills. The UPSA-Brief (UPSA-B) was developed as an abbreviated alternative to the full version of the UPSA ([Mausbach et al., 2007](#)) and contains 2 of the original 5 subscales of the full UPSA (i.e., finance and communications subscales), which allows for shorter administration time (10–15 minutes) and reduced reliance on testing props. An UPSA-Brief Total Score (range = 0–100) is then obtained by summing the subscale scores.

Clinical Global Impressions Improvement Scale (CGI-I) and Severity Scale (CGI-S)

The CGI-I (Guy 1976) is a clinician-rated instrument that measures the degree of the patient's improvement. It is a 7-point scale where 1 = very much improved; 4 = no change; and 7 = very much worse. Baseline for assessing improvement for the CGI-I ratings will be the patient's clinical status at Visit 3. The CGI-S is a similar clinician-rated instrument that measures the overall severity of the patient's illness as compared to the overall study population. It is also a 7-point scale where 1 = normal, not at all ill; 4 = moderately ill; and 7 = among the most extremely ill patients.

Clinician-Administered PTSD Scale (CAPS-5)

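### The cycle dates meant to inform the startle analysis are first collected after the baseline startle test

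*Combined protocol and SAP*

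**What the plan says.** Section V.F describes one diary, kept during Study Period II for dosing: "The patient will also maintain a medication diary to mark the date and time they took their medication". The same paragraph adds the menstrual entries, "Women of child bearing potential will also use the diary to indicate the start date of their menstrual cycles", and gives the reason: "as this information will inform analysis of the startle testing data".

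In the Schedule of Events, the row "Dispense Study Drug & Diary" is first marked at V2 (Day 0) and then at V3 to V8. The row "Startle Paradigm" is marked at V1 and V9 only. Section V.A places the pretreatment testing before Day 0: "These visits will be conducted over a 7-day period prior to the day of randomization". Neither the screening column nor the V1 column lists a diary or a menstrual item.

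Section VII.B gives a general mixed-model approach for repeated measures. It has no startle-specific model, no cycle-phase covariate and no rule for using the diary dates.

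On the startle stimuli, section V.J.3a says: "The pictures and colored shapes will be counterbalanced across subjects". For the cognitive battery, Appendix B assigns forms by visit: "BACS A will be performed at V1 and Version B will be performed at V9".

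**The concern.** The protocol itself treats cycle timing as relevant to startle, and Exploratory Aim 1 compares startle before and after treatment. An adjustment for phase needs phase at both tests. The instrument chosen to supply it does not exist on the day of the first test. Once V1 has passed without the question being asked, only later recall or back-calculation remains. At stake is the accuracy of a covariate in an exploratory analysis. The primary CAPS-5 analysis is untouched.

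**Working it through.** The plan states no figure on this point, so there is none to reproduce. The check sets the visit timings side by side.

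**Inputs.** V1 startle on Days -7 to -1 (section V.A). V2 with first diary on Day 0 (Schedule of Events). V9 on Day 84 plus or minus 3 days, so Days 81 to 87 (section V.F and Schedule of Events). Cycle length is not in the documents; 28 days is assumed, with 24 to 35 days as the range.

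1. **Delay from baseline test to diary.** 0 - (-1) = 1 day to 0 - (-7) = 7 days. The onset preceding the V1 test is always earlier than the first possible diary entry.

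2. **V9.** The diary has run for 81 to 87 days by then, longer than any cycle length in the assumed range. The onset preceding V9 should therefore be in it, and phase at V9 can be dated directly.

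3. **Interval between tests.** Nominal: 84 - (-7) = 91 days. Shortest: 81 - (-1) = 82. Longest: 87 - (-7) = 94. Three 28-day cycles are 84 days, so the second test falls 91 - 84 = 7 days later in the cycle, with a range of 82 - 84 = -2 to 94 - 84 = +10. The nominal remainder depends on cycle length: 91 - 3 x 24 = 19 days for a 24-day cycle, 91 - 3 x 30 = 1 day for 30, and 91 - 2 x 35 = 21 days for 35. Phase is not matched by design.

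4. **Counting back, regular cycles.** Take V1 on Day -7, a 28-day cycle and a first diary onset on Day 10. The preceding onset is 10 - 28 = Day -18, so V1 was 11 days after onset. Now suppose an onset on Day -3 was missed because the diary had not been issued. The next falls on Day 25. Counting back gives 25 - 28 = -3, and once more -3 - 28 = -31, so V1 was 24 days after onset. In both cases phase is recovered exactly.

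5. **Counting back, irregular cycles.** The error in the estimated V1 phase equals the actual minus the assumed length of each cycle counted back. That is one such deviation when the next onset after V1 is in the diary, and the sum of two when it fell between V1 and Day 0. With cycle day uniform and 28 days assumed, the two-cycle case applies to 1/28 = 3.6% of menstruating women if V1 is on Day -1, and to 7/28 = 25% if V1 is on Day -7. At Day -7 the share is 7/24 = 29% for a 24-day cycle and 7/35 = 20% for a 35-day cycle. The documents give nothing on cycle variability, so the error cannot be put in days.

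6. **Between-arm comparison.** Allocation is 1:1 and both arms have the same tests on the same schedule. Any shift common to both arms cancels in the difference of mean changes, and the phase contribution has the same expectation in each arm. A simulation with no drug effect, 30 per arm, 50,000 runs and an assumed common shift of 0, 0.2, 0.3 or 0.5 SD of the change score gave between-arm rejection rates of 5.0%, 5.2%, 4.9% and 5.1%. Type I error holds at its nominal level.

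**The case against.** The case for leaving the plan alone has four parts.

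- **Baseline phase is recoverable.** With regular cycles any one recorded onset fixes the others, and a diary of about 84 days shows each woman's own cycle length. This stands. A reader might infer that adjustment is possible at V9 only, or that back-counting fails for a quarter of women. Neither follows: the 25% is the share needing two cycles counted back when V1 is on Day -7, not a failure rate. What remains is error from irregular cycles.
- **Randomization protects the comparison.** This also stands. A reader might infer that startle change confounds treatment with cycle phase. For a between-arm contrast it does not; phase adds noise and possible chance imbalance. The protection applies only if the analysis is between arms. The hypothesis under Exploratory Aim 1 is worded as improvement from baseline in one arm and none in the other, so the contrast should be written down.
- **Few patients may be affected.** The sample of 60 includes men, and the contraception note in section VIII.B admits surgically sterile and post-menopausal women and users of hormonal contraception. The number of menstruating women is not given.
- **Sites may ask anyway.** Screening includes a medical history and a serum pregnancy test, and the date could be taken then. The protocol does not require it.

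A further tempting reading is that V9 measures retention of cues learned at V1. Section V.J.3a says cues are counterbalanced across subjects and is silent on visits, so different cues at V9 are not excluded. Nothing in the documents supports retention over 12 weeks or gives its size.

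**Conclusion.** The timing gap is real and follows from the Schedule of Events alone: the diary starts 1 to 7 days after the baseline startle test, and nothing else listed captures the preceding onset. The consequence is limited. Baseline phase must be estimated, reliably only for regular cycles, and this adds avoidable error to the phase adjustment for menstruating women in Exploratory Aim 1. The documents do not allow that error to be sized. A between-arm comparison of change is not biased, given the common schedule and 1:1 allocation. The interval of 91 days (82 to 94) rests on stated windows; the phase shifts rest on assumed cycle lengths. This is a minor point, worth making because the protocol says it needs these dates. The missing statement on cue sets is an unspecified detail and carries no weight in this conclusion.

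**What to change.** Record the first day of the last menstrual period on the startle form at V1 and again at V9. Issuing the diary at screening is an alternative, but a weaker one alone. It closes the gap between V1 and Day 0, yet it captures the onset before V1 only if that onset falls after screening. With about one week between the two visits (section V.D) and a 28-day cycle, that is roughly 7/28 = 25% of menstruating women.

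In the statistical section, name the between-arm contrast of startle change as the analysis for Exploratory Aim 1, with cycle phase at both tests as covariates, and say how phase is derived and how men and non-menstruating women are handled. V9 phase is measured after randomization, so report the unadjusted contrast alongside.

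As a separate small clarification, state in section V.J.3a which cue set is used at V1 and which at V9, as Appendix B does for the BACS forms.

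The cost is one extra date field and a few sentences of text. No patient's treatment or visit schedule changes.
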